### **7.3.3 Vital Signs**

The actual values of vital sign parameters, including temperature, heart rate, weight and systolic and diastolic blood pressure, will be presented in a by-subject listing.

### **7.3.4 Electrocardiogram (ECG)**

A by-subject listing will be presented for baseline ECGs and post-baseline unscheduled ECGs (if any).

### **7.3.5 Concomitant Medications and Procedures**

Please refer to [Section 7.1.7](#) for the definition and summary of concomitant medications.

Concomitant procedures will not be summarized. A by-subject listing will be presented.

### **7.3.6 Deaths**

On-treatment deaths are defined as deaths that occur within 30 days of the last dose of study medication. Deaths on treatment and causes for deaths occurring on-treatment, and deaths during follow-up will be summarized.

A by-subject listing of deaths on study will be presented.

## **7.4 Quality of Life Instruments**

Analyses of the QoL instruments (EQ-5D and FACIT-F) will be performed on the ITT analysis set. Additional analyses may be considered as needed.

### **7.4.1 EQ-5D**

The EQ-5D contains a descriptive system with one response for each of 5 dimensions (Mobility, Self-Care, Usual Activities, Pain/Discomfort, and Anxiety/Depression). The first response is coded as 1 (indicating no problems), the second response is coded as a 2 (indicating some problems), and the third response is coded as a 3 (indicating extreme problems). Ambiguous responses (eg, more than one response in a dimension) are treated as missing values. The EQ-5D

also contains a Visual Analog Scale (VAS) for health state ranging from 0 to 100, where 0 represents worst imaginable health state and 100 represents the best imaginable health state.

For each dimension of the descriptive system, the number and percentage of subjects with no problems, some problems, and extreme problems will be reported at each visit.

Summary statistics for the VAS of health state and the change from baseline will be reported for each visit.

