- c. Additional (unscheduled) assessments should be done as clinically indicated. Blood samples should be drawn and results reviewed within 72 hours of the designated clinic visit.
- d. Screening evaluations performed within 7 days of Cycle 1 Day 1 can be used and assessments do not need to be repeated at Cycle 1 Day 1 (predose)
- e. Drawn only on Day 1 of Cycles 3, 5, 7, 11, 15, 19, and ETT. Blood for immunophenotyping, serum for biomarkers, and blood for biomarkers do not need to be collected beyond the ETT visit or treatment discontinuation.
- f. May be either urine or serum, and performed every odd cycle while on treatment.
- g. To be sent to the central laboratory.
- h. Sample may be drawn at screening or Cycle 1 Day 1 (predose). Collection at Cycle 1 Day 1 is preferred. If drawn at screening, a sample is not needed at Cycle 1 Day 1.
- i. This sample will be analyzed centrally and is separate from the documentation of prior del(17p) analysis required for eligibility and stratification.
- j. Additional blood for immunophenotyping/biomarker serum samples may be requested from any subject receiving duvelisib at qualified sites (when feasible) at the time of a drug interruption/hold due to an AE, or for any usual safety event or efficacy event.
- k. Samples on Cycle 1 Day 1 should be drawn predose.
- l. Pharmacogenomics sample (buccal swab) is optional.
- m. QoL assessments to be captured at on Day 1 of Cycles 3, 5, 7, 11, 15, and 19 until disease progression, subject withdrawal, or initiation of additional anticancer therapy, and when possible, at the ETT (if >1 month from last administered questionnaire).
- n. Requests for archival tissue (pretreatment sample) should be initiated at Cycle 1 Day 1. In the event a request is placed but no archival tissue can be located, this sample type is not required.
- o. Subjects who discontinue treatment from duvelisib prior to Cycle 19 Day 1 for reasons other than PD, will maintain the clinical visit schedule through Cycle 19 Day 1 until disease progression, subject withdrawal, or initiation of additional anticancer therapy.
- p. Subjects who, in the judgment of the investigator, may derive benefit from continued treatment, may receive additional cycles of duvelisib beyond Cycle 19 Day 1 until disease progression or unacceptable toxicity. .

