## 6 GENERAL STATISTICAL METHODS AND DATA HANDLING

### 6.1 General Methods

Summary statistics will be presented by treatment group, unless stated otherwise.

Unless otherwise specified, descriptive statistics for continuous data will include the number of subjects with data to be summarized (n), mean, standard deviation, 25% quartile, median, 75% quartile, and minimum and maximum. The same number of decimal places as in the raw data will be presented when reporting the minimum and maximum, one more decimal place than the raw data will be presented when reporting mean and median, and 2 more decimal places than the raw data will be presented when reporting standard deviation.

Descriptive statistics for categorical/qualitative data will include frequency counts and percentages. The total number of subjects in the treatment group will be used as the denominator for percent calculations, unless stated otherwise. All percentages will be presented with one decimal, unless otherwise specified. Percentages equal to 100 will be presented as 100, and percentages will not be presented for zero frequencies.

Descriptive statistics associated with time-to-event analyses will include the number of events, the number of subjects censored, 25% quartile, median, 75% quartile, and 95% confidence interval for median. These statistics will be presented for all time-to-event analyses, unless stated otherwise.

Listings will be provided for selected endpoints.

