### 6.2 Handling of Missing Data

In general, values for missing data will not be imputed unless methods for handling missing data are specified.

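### EQ-5D percentages by visit default to the whole randomised arm although questionnaires stop at progression, so every level shrinks with completion, and by a different factor in each arm

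*SAP*

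**What the plan says.** SAP V4.0 section 7.4 sets the population: "Analyses of the QoL instruments (EQ-5D and FACIT-F) will be performed on the ITT analysis set". For each EQ-5D dimension, section 7.4.1 then states that "the number and percentage of subjects with no problems, some problems, and extreme problems will be reported at each visit". It gives no denominator and no 'missing' category. Its only remark on missingness is that "Ambiguous responses (eg, more than one response in a dimension) are treated as missing values".

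The general rule in section 6.1 is: "The total number of subjects in the treatment group will be used as the denominator for percent calculations, unless stated otherwise". Section 6.2 adds that "values for missing data will not be imputed unless methods for handling missing data are specified", and none is specified for EQ-5D. For continuous data, section 6.1 bases the summary on subjects who have data, so the EQ-5D visual analogue scale (VAS) and the FACIT-F scores use the observed n.

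On collection, Protocol Table 2 footnote m schedules the questionnaires at Cycles 3, 5, 7, 11, 15 and 19 "until disease progression, subject withdrawal, or initiation of additional anticancer therapy, and when possible, at the ETT". Table 4 footnote l says the same for ofatumumab. There is also a baseline form at Screening or Cycle 1 Day 1 (Protocol 6.2.1). Stopping study drug without progression does not end collection, because those subjects keep the visit schedule (Table 2 footnote o, Table 4 footnote o).

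**The concern.** A subject whose disease has progressed is no longer asked to fill in the form but stays in the denominator. The percentage reported for any level at a visit is then the rate among completers multiplied by the fraction of the arm that completed. The design itself assumes that this fraction falls faster on ofatumumab, since progression is the main planned reason for stopping.

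Two things follow. The arms separate on every EQ-5D level with no difference in health state. And two outputs from the same questionnaire rest on different bases: the five dimensions on everyone randomised, the VAS on completers. At stake is the readability of an exploratory table in an open-label trial.

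**Working it through.** **Inputs from the documents.** Median PFS 9 months (ofatumumab) and 15 months (duvelisib), exponential; 185 events; one-sided alpha 0.025; 300 subjects randomised 1:1; 4% dropout per year (SAP 3.2). Cycle 1 is 21 days and later cycles 28 days (SAP 3.1).

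**Assumption.** The documents give no EQ-5D response rates. I assume a common 'no problems' rate among completers of 50%, with a range of 30% to 70%.

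**The plan's own figure.** With HR = 9/15 = 0.6, the Schoenfeld power is Φ(√185 × |ln 0.6| / 2 − 1.960) = Φ(3.474 − 1.960) = 0.935. This agrees with the stated 93% or so, so the PFS inputs are read correctly.

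**Fraction still in collection.** Cycle c Day 1 falls 21 + 28(c − 2) days after Cycle 1 Day 1; divide by 30.44 for months t. The progression-free fraction is 0.5^(t/9) on ofatumumab and 0.5^(t/15) on duvelisib. The percentage reported under the section 6.1 default is the completer rate times that fraction. The last two columns use the 50% rate; gaps are from unrounded values.

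| Visit | Day | Months | Fraction, ofa | Fraction, duv | Reported %, ofa vs duv | Gap (points) |
|---|---|---|---|---|---|---|
| C3 | 49 | 1.61 | 0.883 | 0.928 | 44.2 vs 46.4 | 2.2 |
| C5 | 105 | 3.45 | 0.767 | 0.853 | 38.3 vs 42.6 | 4.3 |
| C7 | 161 | 5.29 | 0.665 | 0.783 | 33.3 vs 39.2 | 5.9 |
| C11 | 273 | 8.97 | 0.501 | 0.661 | 25.1 vs 33.0 | 8.0 |
| C15 | 385 | 12.65 | 0.378 | 0.557 | 18.9 vs 27.9 | 9.0 |
| C19 | 497 | 16.33 | 0.284 | 0.470 | 14.2 vs 23.5 | 9.3 |

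At C19 the fractions are about 43 and 71 of 150 subjects. The three levels sum to about 28% and 47% instead of 100%.

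**Range over the assumed rate, C19.** At 30%: 8.5 vs 14.1, gap 5.6. At 70%: 19.9 vs 32.9, gap 13.0. The ratio of the arms is 0.470/0.284 = 1.65 whatever the rate, and it applies to 'extreme problems' as much as to 'no problems'.

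**When collection stops.** The table assumes that no form is completed at the visit where progression is documented. Disease assessments fall on the same days as the questionnaires (Protocol Table 5), so such a subject may still complete that visit's form. The fraction then moves towards the value at the previous assessment: about 77% vs 85% at C7 and 38% vs 56% at C19. At C3, the first scheduled assessment after baseline, little loss would be expected. On this reading the C19 gap is 5.4, 9.0 or 12.6 points for 30%, 50% or 70%.

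**Other losses.** Multiplying by 0.96^(t/12) for dropout gives 26.9% vs 44.5% at C19 and a gap of 8.8 points (50% rate). If subjects who have not reached C19 by a 27.5-month cutoff also stay in the denominator, and accrual is assumed uniform over 16 months, both arms are multiplied by (27.5 − 16.33)/16 = 0.70. The table then shows 9.9 vs 16.4, with the ratio still 1.65.

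**With the non-missing denominator.** The same inputs give 50% vs 50% at every visit.

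**The case against.** The strongest reply is that nothing turns on this. EQ-5D is exploratory, section 7.4.1 plans description only, and quality of life lies outside the testing hierarchy in section 6.3. The SAP also asks for the number at each level, so the three counts add up to the completers and anyone can recompute the completer rate. The n shown for the VAS exposes the same thing. A programmer might well use the non-missing count by habit. All of this stands and limits the importance of the point. It does not make the planned percentages right, and the programmer's habit would depart from section 6.1.

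The attrition figures are also open to challenge. They use PFS by independent review, whereas a site may stop the questionnaire on its own assessment of progression, and the timing question above moves them. They are approximations, and the first set is the heavier-loss end of a range.

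A reader might infer that the table would show quality of life deteriorating steadily in both arms, or a plain advantage for duvelisib. The documents do not support either. With unchanged health among completers, 'no', 'some' and 'extreme' problems all fall together, which is not a picture of deterioration. Duvelisib would show more 'no problems' and also more 'extreme problems'.

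**Conclusion.** The point holds as a minor error of rule. Section 6.1 supplies a denominator, section 7.4.1 does not override it, and that denominator is unsuitable for a form that stops at progression. That the arms diverge needs only unequal completion, which the design assumes.

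The size is conditional. At Cycle 19 completion is about 28% vs 47%, or 38% vs 56% if forms are still completed at the visit documenting progression. The false gap in 'no problems' under the first reading is about 5.6 to 13.0 points for assumed rates of 30% to 70%; no single value has support in the documents. Type I error, power and the primary and key secondary results are untouched. The baseline table is not affected by loss at progression.

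**What to change.** Add to SAP 7.4.1:

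> At each visit the denominator for each EQ-5D dimension is the number of ITT subjects with a non-missing response for that dimension at that visit. The number completed and the number expected are shown by arm, where expected means subjects who had reached the scheduled visit by data cutoff and for whom the protocol still required a questionnaire (no progression documented before that visit, no withdrawal, death or new anticancer therapy). ETT forms are summarised separately.

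The visit-reached condition keeps subjects not yet at the visit from counting as non-completers. ETT needs its own line because progression itself triggers that visit (Protocol 6.4), so its forms come partly from subjects no longer expected at scheduled visits.

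Label the by-visit percentages as conditional on remaining in collection. The change removes the arithmetic artefact but not the selection of subjects who are still progression-free.

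The cost is a short paragraph and two rows in the table, with no new data and no change to any test.

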#### **7.4.2 FACIT-F**

The FACIT-F contains 5 subscales, Physical Well-Being, Social/Family Well-Being, Emotional Well-Being, Functional Well-Being, and Fatigue (Additional Concerns on eCRF). Each subscale contains multiple items, and each item has a response of 0 to 4. Scores will be computed for each subscale, as well as for the FACIT-F Trial Outcome Index, FACT-G total score, and the FACIT-F total score.

The Physical Well-Being subscale contains 7 items. To compute the subscale score, compute the item score by subtracting each item response from 4 (item score = 4 – item response), sum the item scores, multiply the sum by 7 and divide by the number of items answered. At least 4 questions must be answered. If fewer than 4 questions are answered, then the subscale score will be missing. The Physical Well-Being score ranges from 0 to 28 with higher scores representing better quality of life.

The Social/Family Well-Being score contains 7 questions. To compute the subscale score, sum the item responses, multiply the sum by 7 and divide by the number of items answered. At least 4 questions must be answered. If fewer than 4 questions are answered, then the subscale score will be missing. The Social/Family Well-Being score ranges from 0 to 28 with higher scores representing better quality of life.

The Emotional Well-Being subscale contains 6 items. To compute the subscale score, compute the item score first. For items 1, 3, 4, 5, and 6, subtract each item response from 4 (item score = 4 – item response). For item 2, the item score is the same as the item response (no subtraction is needed). Sum the item scores, multiply the sum by 6 and divide by the number of items answered to compute the subscale score. At least 3 questions must be answered. If fewer than 3 questions are answered, then the subscale score will be missing. The Emotional Well-Being score ranges from 0 to 24 with higher scores representing better quality of life.

The Functional Well-Being score contains 7 questions. To compute the subscale score, sum the item responses, multiply the sum by 7 and divide by the number of items answered. At least 4 questions must be answered. If fewer than 4 questions are answered, then the subscale score will be missing. The Functional Well-Being score ranges from 0 to 28 with higher scores representing better quality of life.

The Fatigue subscale contains 13 items. To compute the subscale score, compute the item score first. For all items except An5 and An7, subtract each item response from 4 (item score = 4 – item response). For items An5 and An7, the item score is the same as the item response (no subtraction is needed). Sum the item scores, multiply the sum by 13 and divide by the number of

items answered to compute the subscale score. At least 7 questions must be answered. If fewer than 7 questions are answered, then the subscale score will be missing. The Fatigue score ranges from 0 to 52 with higher scores representing better quality of life.

To derive the FACIT-F Trial Outcome Index, sum the subscale scores for Physical Well-Being, Functional Well-Being, and Fatigue. If any of these subscale scores is missing, the score for the FACIT-F Trial Outcome Index will be missing. The score ranges from 0 to 108.

To derive the FACT-G score, sum the subscale scores for Physical Well-Being, Social/Family Well-Being, Emotional Well-Being, and Functional Well-Being. If any of these subscale scores is missing, the FACT-G score will be missing. The score ranges from 0 to 108.

To derive the FACIT-F total score, sum all 5 subscale scores. If any subscale score is missing, the FACIT-F total score will be missing. The score ranges from 0 to 160.

For each of the five subscale scores and for each of the FACIT-F Trial Outcome Index, the FACT-G score, and the FACIT-F total score, summary statistics for the actual values and changes from Baseline will be reported at each visit.

## 7.5 Pharmacokinetic Analyses

Plasma samples will be analyzed for duvelisib and IPI-656 (metabolite) concentrations using a validated high performance liquid chromatography-tandem mass spectrometry (LC/MS/MS) method. A listing of the duvelisib and IPI-656 concentrations will be provided; the sample collection date and time, and the date, time and amount of the preceding duvelisib dose administration will be included in the listing.

The PK data collected will be analyzed by standard population PK methods, using appropriate software. Analysis of exposure-response relationships for efficacy and safety endpoints will be conducted. If there is only a limited amount of plasma concentration data from this study, the data may be pooled with the results of other studies to perform the population PK and exposure-response analyses. Further details on these analyses will be outlined in a separate analysis plan. Results of the population PK and exposure-response analysis will be summarized in a separate technical report.

## 7.6 Biomarker Analyses

The following exploratory analyses may or may not be presented formally. If presented, they will be limited to biomarkers for which data from a sufficient number of subjects are available. Further details on these analyses may be outlined in a separate analysis plan, and results may be summarized in a separate technical report.

### 7.6.1 Pharmacodynamic and Potentially Predictive Biomarkers

The relationship between tumor genomics, gene expression, protein expression, and clinical endpoints may be explored as follows:

- Evaluation of serum biomarkers, blood immunophenotype and tumor biomarkers for relationships with duvelisib clinical activity and safety
- Evaluation of tumor genomic features (eg, cytogenetics, FISH, DNA sequence variation, DNA copy number variation, and/or RNA expression) for relationships with duvelisib clinical activity
- Evaluation of the relationship between serum and/or tumor biomarkers and disease progression of duvelisib and ofatumumab

### **7.6.2 Pharmacogenomics**

DNA may be extracted from the pharmacogenomics sample in order to evaluate a subject's germline DNA. This sample may be used to explore the following:

- Evaluate the relationship between germline DNA sequence variations and PK of duvelisib
- Evaluate germline DNA as a control to verify that tumor sequence variations are somatic mutations

## 8 CHANGES IN PLANNED ANALYSES

### 8.1 Changes in Planned Analyses from Protocol Amendment 1 to SAP V1.0

There are no changes from Protocol Amendment 1. More details are provided in the SAP.

### 8.2 Changes in Planned Analyses from SAP V1.0 to SAP V2.0

The main changes from SAP V1.0 to SAP V2.0 are described below.

1. Section 3.5.2 Clarification

Old (V1.0): The second analysis of OS will be performed at the PFS final analysis, which is expected to happen after 185 PFS events have occurred, or approximately 27.5 months after the first subject is randomized.

New (V2.0): The second interim analysis of OS will be performed at the PFS final analysis, which is to happen after 185 PFS events have occurred. If the planned final analysis of PFS is not performed due to early stop for efficacy, then the second interim analysis of OS will be conducted approximately one year after the first interim analysis of OS.

2. New censoring method for event-free survival were specified.
3. Prior irradiation and prior surgery were removed from prior therapy summary.

The following additional analyses/summaries have been added to this version of the SAP:

1. Analysis of ORR of subjects who are on treatment for 60 days or longer
2. Time to OS follow up
3. Time to response
4. Treatment-emergent AEs reported in  $\geq 5\%$  of CLL/SLL subjects and occurred at  $\geq 2\%$  higher incidence in subjects receiving duvelisib (All Causalities)
5. Grade 3 or higher treatment-emergent AEs reported in  $\geq 5\%$  of CLL/SLL subjects and occurred at  $\geq 2\%$  higher incidence in subjects receiving duvelisib (All Causalities)
6. Treatment-emergent AEs by PT (All Causalities, AE onset date within 24 weeks after the first dose of study treatment)
7. Grade 3 or higher treatment-emergent AEs by PT (All Causalities, AEs with onset date within 24 weeks after the first dose of study treatment)
8. Treatment-emergent AEs resulting in discontinuation of study drug (Treatment-Related)
9. Treatment-emergent AEs resulting in death (Treatment-Related)
10. Treatment-emergent SAEs by PT (All Causalities).
11. Treatment-emergent SAEs by PT (Treatment-Related)
12. Deaths on treatment
13. Deaths during follow-up

14. A by-subject listing of treatment-emergent AEs resulting in dose hold
15. A by-subject listing of treatment-emergent AEs resulting in dose reduction
16. A by-subject listing of deaths on study
17. A summary table and a listing of the discrepancies in data for stratification factors between those captured in the IRT and those reported on the eCRF
18. Comparison of del[17p] values captured from central lab and local lab
19. The following biomarkers will be summarized as baseline characteristics:
  - del[17p] (captured from central lab, presence vs absence vs indeterminate)
  - del[17p] (captured from local lab, presence vs absence vs indeterminate)
  - del[17p] and/or TP53 mutation (del[17p] and/or TP53 mutation, del[17p] captured from central lab, either or both present vs neither present vs indeterminate)
  - del[17p] and TP53 mutation (del[17p] and TP53 mutation, del[17p] captured from central lab, both present vs either vs neither present vs indeterminate)
  - TP53 mutation (presence vs absence vs indeterminate)
  - IgHV status (mutated vs unmutated vs indeterminate)
  - CD38 (Positive ( $\geq 30\%$ ) vs Negative vs indeterminate)
  - ZAP70 (Positive ( $> 19\%$ ) vs Negative ( $\leq 19\%$ ) vs indeterminate)
20. Subgroup analyses of PFS, OS and ORR based on the following factors:
  - Time from last dose of most recent prior anti-cancer therapy to randomization  $< 12$  months: yes vs no
  - del[17p] (captured from central lab) or TP53 mutation (either or both present vs neither present )

